## **7.9 General Concomitant Medication and Supportive Care Guidelines**

If the subject must use other concomitant medications (including all pain medications; vitamins; herbal and nutritional supplements; and over-the-counter medications) during the period from 28 days before treatment through to 30 days after the decision to permanently discontinue study treatment, it is the responsibility of the investigator to ensure that details regarding the medication are recorded in the source documents.

Drugs used to control bone loss (e.g. bisphosphonates, denosumab) are allowed if started prior to screening activities but may not be initiated or exchanged during the course of the study. Transfusions, hormone replacement, and short-term systemic steroid treatment should be utilized as indicated by standard clinical practice while the subject is enrolled in the study.

Antacids, H2 blockers, or proton-pump inhibitors (PPIs) should be taken at least 2 hours (preferably 4 hours) after taking cabozantinib but at least 14 hours before the next dose of cabozantinib if possible.

### **7.9.1 Guidelines for Management of Potential Adverse Events**

Subjects will be monitored for AEs from the time of signing informed consent through their last follow-up visit (30 days after the date of the last dose of cabozantinib treatment.) Subjects will be instructed to notify their physician immediately at the onset of any AE. Seriousness, severity grade, and relationship to study treatment of AEs will be determined by the investigator. AE severity will be graded by the investigator in accordance with CTCAE v.4.0.

Management of severe or intolerable adverse reactions may require temporary dose reduction and/or interruption for cabozantinib.

### **7.9.2 Cabozantinib**

The most frequent AEs experienced by  $\geq 20\%$  of subjects treated with cabozantinib in descending order of frequency were diarrhea, fatigue, decreased appetite, nausea, weight decreased, PPES, vomiting, constipation, hypertension, dysgeusia, dysphonia, asthenia, and dyspnea. For a full description of the safety profile of cabozantinib, refer to the cabozantinib Investigator's Brochure.

Other medically important but less frequent AEs including arterial thrombotic AEs (e.g. transient ischemic attack [TIA], and myocardial infarction [MI]) and venous thrombotic AEs (e.g. deep vein thrombosis [DVT] and pulmonary embolism), severe hemorrhagic events, proteinuria, wound healing complications, gastrointestinal (GI) perforation, abscesses including intra-abdominal and pelvic abscess, GI and non-GI fistula formation, osteonecrosis, and reversible posterior leukoencephalopathy syndrome (RPLS).

Adverse events associated with laboratory abnormalities experienced by  $\geq 5\%$  of subjects treated with cabozantinib in descending order of frequency were anemia, AST increased, ALT increased, hypothyroidism, hypokalemia, hypomagnesemia, thrombocytopenia, hypocalcemia, hypophosphatemia, lactate dehydrogenase (LDH) increased, lipase increased, neutropenia, hyponatremia, ALP increased, leukopenia, and hyperglycemia.

Adverse events may occur within the first few weeks in the course of treatment with cabozantinib, as cabozantinib is expected to reach steady state exposure at approximately 2 weeks following first dose. Events that generally have an early onset include hypocalcemia, hypokalemia, thrombocytopenia, hypertension, PPES, abdominal pain, mucosal inflammation, constipation, diarrhea, and vomiting.

Adverse events should be managed with supportive care at the earliest signs of toxicity. Dose reductions and treatment interruptions should be considered. Dose reductions are recommended for events that, if persistent, could become serious or intolerable (See Table 7.2).

Cabozantinib should be discontinued for the following AEs: visceral perforation or fistula formation, severe hemorrhage, serious arterial thromboembolic events, nephrotic syndrome, hypertensive emergency, persistent uncontrolled hypertension despite optimal medical management, and RPLS.

### **7.9.3 Gastrointestinal Disorders**

Gastrointestinal perforation, GI fistula, and intra-abdominal and pelvic abscess: After starting treatment with cabozantinib, subjects should be monitored for early signs of GI perforation such as

abdominal pain, nausea, emesis, constipation, and fever especially if known risk factors for developing GI perforation or fistula (Turnage and Badgwell 2016) are present. Discontinue cabozantinib and initiate appropriate management in subjects who have been diagnosed with GI perforation or fistula.

**Diarrhea:** Subjects should be instructed to notify their physician immediately at the first signs of poorly formed or loose stool or an increased frequency of bowel movements. Guidelines for the evaluation and management of diarrhea are shown in Table 7.4. Administration of antidiarrheal/antimotility agents is recommended at the first sign of diarrhea as initial management. Some subjects may require concomitant treatment with more than one antidiarrheal agent. When therapy with antidiarrheal agents does not control the diarrhea to tolerable levels, cabozantinib should be temporarily interrupted or dose reduced. When the diarrhea is controlled, retreatment with cabozantinib may be acceptable per investigator decision. In addition, general supportive measures should be implemented such as continuous oral isotonic hydration, correction of fluid and electrolyte abnormalities, small frequent meals, and stopping lactose-containing products, high-fat meals, and alcohol.

Recurrent or prolonged diarrhea can be associated with anal or perianal skin erosions which increase the risk for anal abscesses, fistulas, or proctitis. Good personal hygiene should be emphasized. Regular examinations of the perianal region should be performed whenever diarrhea has occurred during treatment with cabozantinib. Infections of the perianal region should be treated per local guidelines.

**Table 7.4: Management of Diarrhea Associated with Cabozantinib**

Status	Management
Tolerable Grade 1-2 (duration < 48 h)	
 
Continue with study treatment and consider dose reduction
 
Initiate treatment with an antidiarrheal agent (e.g. loperamide 4 mg followed by 2 mg after each episode of diarrhea [maximum: 16 mg loperamide per day])
 
Dietary modifications (e.g. small lactose-free meals, bananas and rice)
 
Intake of isotonic fluids (1-1.5 L/day)
 
Re-assess after 24 hours: 
 
Diarrhea resolving to baseline bowel habits: gradually add solid foods and discontinue or decrease antidiarrheal treatment after 12 h diarrhea-free interval
 
Diarrhea not resolving: Continue/resume antidiarrheal treatment
 
 
 

Intolerable Grade 2, Grade 2 > 48 h, or ≥ Grade 3	
 
• Interrupt study treatment
 
• Ask subject to attend clinic
 
• Rule out infection (e.g. stool sample for culture) 
 
○ Administer antibiotics as needed (e.g. if fever or Grade 3-4 neutropenia persists > 24 h)
 
 
 
• Administer fluids (1-1.5 L/day orally or IV, as appropriate) for hydration or to correct electrolyte abnormalities
 
• For Grade 3-4 or complicated lower grade diarrhea consider hospitalization and IV hydration
 
• Re-assess after 24 h 
 
○ Diarrhea resolving to baseline bowel habits or Grade ≤ 1: consider restarting study treatment at reduced dose
 
○ Diarrhea not resolving: Start and or continue antidiarrheal treatment (e.g. loperamide 4 mg followed by 2 mg after each episode of diarrhea [maximum: 16 mg loperamide per day]). Consider starting second line antidiarrheal or referral to gastroenterologist
 
 
 

---	--

**Nausea and vomiting:** Antiemetic agents are recommended as clinically appropriate for treatment or prophylaxis of nausea and vomiting, along with supportive care. Dehydration and electrolyte abnormalities may be associated with vomiting and monitoring for and correction of fluid and electrolyte disturbances should be implemented. Antiemetic medications should be assessed for potential drug interactions (refer to Section 8.3 for further details).

#### **Dehydration**

Dehydration events have been identified with comparable incidence and occurring in a shorter time to onset in the prostate cancer studies than previously experienced with cabozantinib in other tumor types. Extra monitoring/medical management including electrolyte monitoring and/or early dose reduction of patients exhibiting dehydration symptoms and those with risk factors for dehydration is indicated.

#### **7.9.4 Non-Gastrointestinal Fistula**

Complications from radiation therapy especially of the thoracic cavity including mediastinum have been identified as a possible predisposing risk factor for non-GI fistula formation in subjects undergoing treatment with VEGF pathway inhibitors.

Discontinue cabozantinib and initiate appropriate management in subjects who have been diagnosed with a non-GI fistula.

#### **7.9.5 Hemorrhage**

Hemorrhagic events, including serious and sometimes fatal events, have been reported with cabozantinib. Subjects should be monitored for bleeding events with serial complete blood counts and physical examination while on study. The risk of hemorrhage in cabozantinib-treated subjects with brain metastases has not been thoroughly analyzed. Subjects enrolled with treated and stable brain metastases should be monitored with a high index of suspicion if symptoms that could be due to a CNS hemorrhage occur.

Cabozantinib should be held for 5 days before and an additional 5 days after procedures, including biopsies.

Cabozantinib should be discontinued in subjects with serious and life-threatening bleeding events or recent hemoptysis ( $\geq 2.5$  mL of red blood).

### 7.9.6 Thromboembolic events

Thromboembolic events are frequent in cancer subjects due to procoagulant changes induced by the malignancy or anticancer therapy. DVT and pulmonary embolism have been observed in clinical studies with cabozantinib, including fatal events. Subjects who develop a pulmonary embolism and/or DVT should have study treatment interrupted until therapeutic anticoagulation is established. Treatment with cabozantinib may be resumed in subjects with pulmonary embolism or DVT if it is determined that the event is uncomplicated and that the subject is deriving clinical benefit from cabozantinib treatment and that anticoagulation does not place them at a significant risk that outweighs the benefit of resuming treatment per discretion of the investigator and according to individual protocols. Therapeutic doses of LMWH or the direct factor Xa oral inhibitors rivaroxaban, edoxaban, or apixaban are allowed for management of thrombotic events. Other oral anticoagulants including coumarin agents (e.g., warfarin), direct thrombin inhibitors (e.g., dabigatran), direct factor Xa inhibitor betrixaban, platelet inhibitors (e.g., clopidogrel), and chronic use of aspirin above low dose levels for cardioprotection per local applicable guidelines are not allowed, until 4 weeks after cabozantinib has been permanently discontinued. See Section 7.2 for additional restrictions on anticoagulation therapy.

Arterial thrombotic events (e.g. TIA, MI) have been observed in studies with cabozantinib. Further treatment with cabozantinib should be discontinued in subjects who develop an acute MI, cerebral infarction, or any other clinically significant arterial thromboembolic complication.

### 7.9.7 Hypertension

**Table 7.5: Management of Hypertension Associated with Cabozantinib**

Event	Management
Subjects NOT receiving optimized anti-hypertensive therapy	

> 140 mm Hg (systolic)a and < 160 mm Hg
 
OR
 
> 90 mm Hg (diastolic) and < 110 mm Hg
	
 
Optimize antihypertensive medications by adding new or additional antihypertensive medications and/or increase dose of existing medications.
 
Reduce cabozantinib treatment by one dose level if optimal antihypertensive therapy (usually to include 3 agents) does not result in BP <140 mm Hg systolic or <90 mm Hg diastolic
 
If subject is symptomatic interrupt cabozantinib treatment
 

≥ 160 mm Hg (systolic)
 
OR
 
≥ 110 mm Hg (diastolic)
	
 
• Reduce cabozantinib by one dose levelb or interrupt cabozantinib treatment per Investigator discretion.
 
• Add new or additional anti-hypertensive medications and/or increase dose of existing medications and monitor subject closely for hypotension. If optimized antihypertensive therapy (usually to include 3 agents) does not result in BP < 140 mm Hg systolic or < 90 mm Hg diastolic, cabozantinib treatment should be dose reduced further or interrupted.
 
• Cabozantinib treatment should be dose interrupted if upper limits of systolic BP (≥ 160 mm Hg) are sustained and not adequately manageable or if systolic BP is > 180 mm Hg or diastolic BP > 110 mm Hg, or if subject is symptomatic.
 
• Re-start cabozantinib treatment at the most tolerable dose and re-escalate only if BP falls to and is sustained at < 140 mm Hg systolic and < 90 mm Hg diastolic.
 

Hypertensive emergency	
 
• Discontinue cabozantinib treatment.
 

a Permitted dose levels are defined by individual protocols.
 
b Hypertensive emergency is defined as uncontrolled elevated BP with clinical evidence of progressive or impending end-organ damage (e.g., myocardial infarction/ischemia, intracranial hemorrhage, cerebral ischemia, pulmonary edema, encephalopathy, kidney damage).
	

The table above provides treatment guidelines for hypertension deemed related to cabozantinib. Blood pressure should be monitored in a constant position visit to visit, either sitting or supine in a relaxed setting. Decisions to reduce or interrupt the dose of study treatment must be based on BP readings taken by a medical professional and must be confirmed with a second measurement at least 5 minutes following the first measurement.

Cabozantinib should be discontinued in subjects with hypertensive emergency.

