9. The subject has uncontrolled, significant intercurrent or recent illness including, but not limited to, the following conditions:
  - a. Cardiovascular disorders:
    - i. Congestive heart failure New York Heart Association Class 3 or 4, unstable angina pectoris, serious cardiac arrhythmias.
    - ii. Uncontrolled hypertension defined as sustained blood pressure (BP)  $>140$  mm Hg systolic or  $>90$  mm Hg diastolic despite optimal antihypertensive treatment.
    - iii. Stroke (including transient ischemic attack [TIA]), myocardial infarction (MI), or other ischemic event, or thromboembolic event (*e.g.* deep venous thrombosis, pulmonary embolism) within 6 months before first dose.
  - b. Gastrointestinal (GI) disorders including those associated with a high risk of

perforation or fistula formation:

- i. The subject has evidence of tumor invading the GI tract, active peptic ulcer disease, inflammatory bowel disease (*e.g.*, Crohn's disease), diverticulitis, cholecystitis, symptomatic cholangitis or appendicitis, acute pancreatitis, acute obstruction of the pancreatic duct or common bile duct, or gastric outlet obstruction.
  - ii. Abdominal fistula, GI perforation, bowel obstruction, or intra-abdominal abscess within 6 months before first dose.  

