### 7.8.1 Dosing Delays/Dose Modifications

The following should be taken into consideration in decisions regarding dose modifications (reductions or interruption):

- As a general approach all AEs should be managed with supportive care at the earliest signs of toxicity considered related to the study treatment. Should this be ineffective, dose interruptions and/or reductions should be considered to prevent worsening of toxicity.
- The assigned starting dose for cabozantinib is 40 mg/day. Two dose reduction levels of cabozantinib is permitted (see Table 7.2).
- Dose modification criteria for cabozantinib are shown in Table 7.2. Dose interruptions and/or reductions should be implemented for unacceptable toxicity. Doses may be

modified at any time while a subject is on treatment.

- Dose reductions or interruptions may also occur in the setting of lower grade toxicity than defined in Table, if the investigator feels it is in the interest of a subject's safety and will optimize drug tolerability.
- Interruption of cabozantinib treatment for cabozantinib-related AEs may occur at any time per investigator discretion. If treatment is interrupted due to related AEs for more than 6 weeks, cabozantinib should be discontinued unless there is unequivocal evidence that the subject is benefitting. In this situation, a subject may be able to restart therapy with a dose reduction upon resolution of the toxicity per the discretion of the investigator.
- Dose interruptions for reason(s) other than related AEs (e.g., surgical procedures) can be longer than 6 weeks per the discretion of the investigator.

General management of cabozantinib dosing related to AEs is in Section 7.8.1 and additional guidelines for the management of specific AEs are provided in Section 7.9

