**Table 7.3: Dose Modifications of Cabozantinib for Treatment-Related AEs**

Event	Management
Grade 1 AEs	Add supportive care as indicated. Continue cabozantinib treatment at the current dose level if AE is manageable and tolerable.
Grade 2 AEs which are tolerable and are easily managed	Continue cabozantinib treatment at the current dose level with supportive care.
Grade 2 AEs which are intolerable and cannot be adequately managed	At the discretion of the Investigator, cabozantinib should be dose reduced or interrupted.  Note: It is recommended that dose holds be as brief as possible.

Grade 3 AEs (except clinically non-relevant laboratory abnormalities)	Cabozantinib should be interrupted unless the toxicity can be easily managed with a dose reduction and optimal medical care.  Note: It is recommended that dose holds be as brief as possible.
Grade 4 AEs (except clinically non-relevant laboratory abnormalities)	Subjects should have cabozantinib interrupted immediately. Discontinue cabozantinib unless the following criteria are met: 
 
• Subject is deriving clear clinical benefit as determined by the Investigator, and approved by the Principal Investigator.
 
• Toxicity can be managed with a dose reduction following recovery to Grade 1 (or baseline) and optimal medical care .
 

Note: The dose delay and modification criteria for specific medical conditions are provided in Section 7.7.1	

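### Table 7.5 joins the systolic and diastolic targets for cabozantinib dose reduction with *or* where *and* is almost certainly meant: a minor wording error in a safety dosing rule

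*Combined protocol and SAP*

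**What the plan says.** Row 1 of Table 7.5 covers patients with systolic pressure above 140 and below 160 mm Hg, or diastolic pressure above 90 and below 110 mm Hg. After antihypertensive treatment has been optimised, the instruction is "Reduce cabozantinib treatment by one dose level if optimal antihypertensive therapy (usually to include 3 agents) does not result in BP" under 140 systolic *or* under 90 diastolic. Symptomatic patients in this row are interrupted whatever the target.

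Row 2 covers 160 systolic or 110 diastolic and above. Its second step repeats the target with *or*: if optimised therapy does not reach it, "cabozantinib treatment should be dose reduced further or interrupted". Its last step uses a different conjunction: "Re-start cabozantinib treatment at the most tolerable dose and re-escalate only if BP falls to and is sustained at" below "140 mm Hg systolic and" below 90 diastolic.

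Exclusion 9.a.ii in Section 4.3 also bears on the meaning: "Uncontrolled hypertension defined as sustained blood pressure (BP") above 140 systolic or above 90 diastolic despite optimal treatment. One raised component is enough there.

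The text after the table says "The table above provides treatment guidelines for hypertension deemed related to cabozantinib". It also requires a professional's reading and a confirmatory second one before any dose change. It does not say how the two components combine.

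**The concern.** The target sits inside a negative: reduce if therapy does *not* achieve A *or* B. In ordinary logic that condition holds only when both A and B fail. A patient can therefore enter row 1 on one raised component, remain raised on that component after about three agents, and still count as having reached the target because the other component was never high.

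What is at stake is consistent dosing for safety. Section 7.9.2 lists hypertension among the events seen in at least 20% of treated subjects, and Section 4.7 expects about eight sites, so the table will be used. A site applying the words as written would leave a patient with isolated systolic or diastolic hypertension at the current dose. A site assuming *and* would reduce by one level.

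**Working it through.** No figure in the plan needs reproducing. The check writes the table's conditions as logic and evaluates them at specific readings. S is systolic and D is diastolic pressure, in mm Hg.

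**Conditions and sources**
- Row 1 entry (Table 7.5): 140 < S < 160 or 90 < D < 110.
- Reduction as written (Table 7.5, row 1; same target in row 2, second step): not (S < 140 or D < 90), which equals S ≥ 140 and D ≥ 90.
- Reduction with *and*: not (S < 140 and D < 90), which equals S ≥ 140 or D ≥ 90.
- Uncontrolled for eligibility (Section 4.3, 9.a.ii): S > 140 or D > 90.
- Re-escalation target (Table 7.5, row 2, last step): S < 140 and D < 90.

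**Results for an asymptomatic patient on optimal therapy**

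| Reading | Row 1 range | Reduce, as written | Reduce, with *and* | Uncontrolled per 9.a.ii | Re-escalation target met |
|---|---|---|---|---|---|
| 155/85 | yes | no | yes | yes | no |
| 135/100 | yes | no | yes | yes | no |
| 150/95 | yes | yes | yes | yes | no |
| 135/85 | no | no | no | no | yes |
| 140/85 | no | no | yes | no | no |
| 135/90 | no | no | yes | no | no |
| 140/90 | no | yes | yes | no | no |

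The first two lines carry the point: in the row 1 range and uncontrolled by the eligibility definition, yet no reduction as written. The third and fourth are controls, where both wordings agree. The last three show the boundary, which matters for the cost of the fix.

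**Coverage.** There are three uncontrolled states: systolic only, diastolic only, both. As written the trigger acts on 1 of 3; with *and*, on 3 of 3. The same result on a grid of whole-number readings (S from 100 to 159, D from 60 to 109):
- Row 1 readings: 19 × 50 + 60 × 19 − 19 × 19 = 950 + 1,140 − 361 = 1,729.
- Triggered as written: 20 × 20 − 1 = 399 (the pair 140/90 is not in row 1).
- Triggered with *and*: all 1,729.

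The counts depend on the chosen grid. They show what the rule covers, not how often patients fall there.

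**Row 2.** Readings of 165/85 and 135/112 also miss the literal second-step trigger. Other row 2 steps still act on them: an initial reduction or interruption, then interruption if systolic pressure of 160 or more is sustained and not manageable, or if diastolic pressure exceeds 110. The gap that matters is therefore the asymptomatic row 1 patient.

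**The case against.** The strongest reply is that the literal parse defeats the row's own purpose. Row 1 entry names the components as systolic or diastolic, and the target repeats them in that order. Read component by component, a patient who enters on a systolic of 155 must reach a systolic below 140, so 155/85 does trigger a reduction. Under the literal parse that patient would already be on target at entry, and optimising antihypertensives would have no goal. This is good evidence of intent, and I accept it as such. Nothing in the text compels that reading, however, and a dosing rule should not depend on the site working it out.

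The second reply is that other provisions soften the effect, and they do. The table is described as guidance. Section 7.8.1 says "Dose reductions or interruptions may also occur in the setting of lower grade toxicity than defined in Table" where the investigator thinks it serves the patient's safety. For intolerable Grade 2 events that cannot be adequately managed, Table 7.3 says "At the discretion of the Investigator, cabozantinib should be dose reduced or interrupted". Section 7.9.2 recommends reductions for persistent events that could become serious or intolerable. These provisions permit or encourage the right action; they do not correct the stated trigger.

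Third, exclusion 9.a.ii governs entry to the trial, not dosing. That is correct. It is used here only to show how the protocol understands uncontrolled pressure elsewhere.

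**Conclusion.** The point holds as a minor wording error in an operative safety rule. Two target statements in Table 7.5 say *or*. Taken literally, they require no reduction for isolated systolic or diastolic hypertension in an asymptomatic row 1 patient on optimal therapy. This is inconsistent with row 1 entry, the re-escalation target and the eligibility definition. The conclusion rests on the literal reading of the negated target. The number of patients affected cannot be computed, because the documents give no rate of hypertension that stays uncontrolled on about three agents. Sample size and the primary analysis are unaffected.

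A reader might infer two stronger claims that the documents do not support.
- *That the literal reading takes a patient straight to discontinuation, bypassing the reductions in Table 7.2.* Section 7.9.2 does list persistent uncontrolled hypertension as a reason to stop, and Section 7.10 makes such conditions binding. But the paragraph just before that list recommends dose reductions and points to Table 7.2, and Section 13.2.4 repeats the recommendation. The claim would also need a site to call the same reading on target in one section and uncontrolled in another.
- *That row 2 contradicts itself.* At 155/85 after a row 2 reduction, the literal text says neither reduce further nor re-escalate. Holding a dose and raising it are different decisions, and a stricter threshold for raising it is coherent. The wording is inconsistent, but the instructions can both be followed.

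**What to change.** In Table 7.5, change *or* to *and* in the two target statements (row 1, and row 2 second step), so that both require systolic below 140 and diastolic below 90 mm Hg, matching the re-escalation step. No new discontinuation row is needed.

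The change is two words and adds no patients, visits or procedures. The price is a few more one-level reductions in row 1, and further reductions or interruptions in row 2, for hypertension confined to one component. It also widens a small boundary mismatch. As written, only 140/90 exactly meets the reduction trigger without exceeding the eligibility limits. With *and*, so does any reading with one component exactly at its limit and the other not above its own, such as 140/85 or 135/90. If the team does not want to act on those readings, it can set the target at 140 or below and 90 or below, which removes the mismatch with row 1 entry and exclusion 9.a.ii; the re-escalation step would then remain slightly stricter.
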